Data from randomized clinical trials and observational studies suggest relapse is common if rituximab is discontinued indefinitely. Among patients in the RAVE trial who achieved complete remission following treatment with rituximab, 32% had a relapse within 18 months(9).

Furthermore, Alberici *et al* reported that 41% of patients who received maintenance rituximab every 6 months for 24 months relapsed at a median of 34.4 months following discontinuation of therapy(17). Predictors of relapse included return of B cells and change from ANCA negativity to positivity(17).

Survival of ANCA vasculitis patients undergoing rituximab-induced continuous B cell depletion

A prospective and longitudinal clinical trial is needed to determine the ideal treatment strategy for long-term maintenance of remission. Here we propose to compare 2 strategies once patients have

been in sustained remission on scheduled rituximab dosing with a goal of undetectable B cells for greater than or equal to 2 years. Target enrollment is 200 subjects over 48 months from the time the first patient is enrolled to be followed for a common close out date of 36 months after the last subject is enrolled.

The study design is an open-label, single center, randomized and two-arm controlled trial to evaluate the optimal maintenance of remission strategy that provides the best relapse-free survival in patients with ANCA vasculitis as determined by relapse-free remission at 18, 24 and 36 months from enrollment. Subjects with ANCA vasculitis in sustained remission on regularly scheduled rituximab infusions with a goal of undetectable B cells for a minimum of two years who meet specific entry criteria will be randomized with stratification based on ANCA subtype and rituximab vintage (i.e., duration of continuous rituximab prior to enrollment) to one of two arms :

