- 1. Primary Aim: To determine whether a rituximab-dosing protocol based on: 1) reconstitution of peripheral B cells or 2) a serologic ANCA flare is more efficacious in preventing relapse in patients with ANCA vasculitis.** Eligible patients will have completed a minimum of 2 years of rituximab maintenance therapy without relapse. The endpoint will be disease relapse defined as a BVAS/WG ≥ 2 . Analysis will also be stratified based on ANCA subtype (due to differences in relapse between patients with MPO and PR3 ANCA) and rituximab vintage.
- 2. Secondary Aim 1: To determine whether a rituximab-dosing protocol based on: 1) reconstitution of peripheral B cells or 2) a serologic ANCA flare is associated with more serious adverse events.** Serious adverse events of interest include those related to vasculitis activity and those that develop as a consequence of rituximab therapy. The main rituximab-associated serious adverse events noted in our cohort are infection, late-onset of neutropenia, and infusion reactions(10)
- 3. Secondary Aim 2: To determine whether a rituximab-dosing protocol based on: 1) reconstitution or peripheral B cells or 2) a serologic ANCA flare is associated with a greater composite of disease relapse (BVAS/WG ≥ 2) and serious adverse events.**
- 4. Secondary Aim 3: To determine whether a rituximab-dosing protocol based on: 1) reconstitution of peripheral B cells or 2) a serologic ANCA flare is associated with greater rituximab utilization during the study period.** While effective, rituximab therapy is costly and increases health care expenditures. Evaluation of the relative cost of the 2 dosing-strategies will assist in the application of these dosing-strategies to the broad population of patients with ANCA vasculitis.

III. Subject Selection

Patients with ANCA vasculitis who are seen at MGH will be recruited as subjects and inclusion and exclusion criteria are detailed below.

A. Inclusion and exclusion criteria

Inclusion criteria:

1. All patients must be able and willing to give written informed consent and comply with the requirements of the study protocol.

2. Diagnosis: ANCA vasculitis as defined by a positive MPO- and/or PR3-ANCA test together with clinical features characteristic of ANCA-positive diseases as detailed in the 2012 Chapel Hill Consensus Conference Definitions(18).
3. eGFR \geq 20 cc/min/1.73m²
4. Age: 18-82 years old

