When a potential subject is identified, the research nurse will initially explain the study to the patient after their clinical visit with [name], [name], or [name]. If the patient expresses further interest in participating in the study, [name], [name], or [name] and the research nurse will then review the study details with the patient. The patient will be provided the opportunity to take the consent form home to further review and will follow-up with the research nurse or investigator within 14 days. If they decline participation, they will continue to receive their standard of care as deemed appropriate by their treating clinician. Massachusetts General Hospital is expecting to enroll up to 200 subjects over 36 months.

C. Treatment assignment and randomization

Each subject will be stratified prior to randomization to ensure MPO- and PR3-ANCA serotypes and duration of rituximab therapy are approximately equal within each arm. Randomization will occur using random permuted blocks to assign each subject to one of two arms:

1. Treatment upon B cell return, OR
2. Treatment upon a significant rise in ANCA titer as defined above.

V. Study Procedures

A. Study visits and parameters to be measured

1. Potential subjects will be identified during a clinical visit. Medical records will be reviewed by study staff and if found eligible then the potential subjects will be offered the opportunity to participate in the study at that visit. Potential subjects will have 14 days to decide on participation.
2. "Day 0" is defined as the date of the last rituximab infusion prior to randomization and must be 6 months +/- 14 days from Study visit 1. Existing data will be collected from this date once enrolled and randomized.
3. **Study Visit 1: Enrollment and Randomization**
 - a. Patients who agree to participate and have signed and dated the consent form will be randomly assigned to one of two treatment arms:

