Rituximab (Rituxan, Genentech), which is FDA-approved for GPA and MPA, will be used in the study.

C. Devices to be used

Not applicable

D. Procedures/surgical interventions

Not applicable

E. Data to be collected and when the data is to be collected

At present, there is no standard of care for maintenance of remission in ANCA vasculitis beyond the two-year mark; thus, the role of continuous versus intermittent B cell depletion requires investigation. Efficacy and toxicity are the foci of our outcome analysis for this study and will be assessed through analysis of primary and secondary endpoints.

The following variables will be collected at EACH study visit:

1. VDI (every 6 months)
2. Modified BVAS/WG
3. Laboratory data at baseline and at subsequent visits
 - a. Complete Blood Count
 - b. Comprehensive Metabolic Panel
 - c. eGFR
 - d. ANCA titer
 - e. ESR
 - f. CRP

- g. Immunoglobulin levels (every 6 months)
 - h. Urinalysis
 - i. Urine Hcg for women of child bearing potential (only at screening and when reinfused with rituximab)
 - j. Flow cytometric analysis of peripheral B and T lymphocyte markers
4. Concomitant medications at each visit
 5. Adverse events assessment

VI. Biostatistical Analysis

A. Specific data variables being collected for the study (e.g. data collection sheets)

Data variables collected are listed above and we will also verify contact information at each visit to ensure appropriate follow-up.

B. Study endpoints

Primary endpoints:

1. Disease flare defined as a BVAS/WG ≥ 2 . A subgroup analysis will be performed by ANCA subtype.

Secondary endpoints:

1. Proportion of patients with serious adverse events (SAEs), including all episodes of Late Onset Neutropenia (LON, absolute neutrophil count < 1000 cells/mm³)
2. The composite of disease flare (defined as BVAS/WG ≥ 2) and serious adverse events.
3. Total rituximab utilization during the study period
4. Accrued organ damage as assessed by the Vasculitis Damage Index (VDI)
5. Patient quality of life assessment using the SF-36v2 and EQ-5D-5L surveys every 6 months
6. Number of major (modified BVAS-WG ≥ 3) relapses
7. Survival
8. Hypogammaglobulinemia (IgG < 400 mg/dL)
9. All infections

C. Statistical methods

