Data will be analyzed by the intention-to-treat principle. Randomization will be stratified on ANCA subtype (MPO vs PR3) and rituximab vintage (< 3 years vs > 3 years). Rituximab vintage is the duration of continuous rituximab therapy administered prior to enrollment in the study. We have contracted with the company StudyTRAX to perform randomization on stratified variables via random permuted blocks.

Continuous data will be summarized using descriptive statistics. Continuous data will be assessed using the t-test or Wilcoxon rank-sum test as appropriate. Categorical data will be assessed using the Chi-square and the Fisher exact tests as appropriate. The probability of remaining free of relapse will be estimated using the Kaplan-Meier method. The difference between the two

treatment strategies will be assessed using the log-rank test. *P* values of 0.05 will be considered significant.

D. Power analysis

Using a two-sided logrank test with an alpha level of 0.05, a projected relapse risk of 15% in the superior group and 30% in the inferior group, and an estimated enrollment time of 36 months, it was determined that 180 patients are required to detect a significant difference with a power of 0.80. We aim to enroll 200 patients in the study.

VII. Risks and Discomforts

Subjects may experience side effects while receiving rituximab, which is given as part of their regular medical care for their GPA or MPA. As per the entry criteria, subjects have been on rituximab for 2 years prior to enrollment, the side effects have been discussed in detail and a signed consent for rituximab is obtained for every patient receiving rituximab at the first dose and annually thereafter.

The effects of rituximab on a fetus are unknown and may be harmful. Individuals of childbearing potential should use effective birth control during treatment and for 12 months after their last rituximab infusion. Prior to any infusion of rituximab to a woman of childbearing potential, a urine pregnancy test is performed and recorded. If a woman is found to be pregnant, she will then be removed from the study and followed based on best medical judgment as deemed appropriate by the clinician investigator.

A. Complications of surgical and non-surgical procedures

Not applicable

B. Drug side effects and toxicities

Common side effects of Rituxan

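### The primary log-rank test names no strata although randomisation is stratified on ANCA subtype and rituximab vintage, and the Primary Aim's stratified analysis has no stated role

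*Combined protocol and SAP*

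**What the plan says.** **Randomisation.** Three places in the combined protocol and SAP stratify it on the same two factors.
- Section I (study design): subjects "will be randomized with stratification based on ANCA subtype and rituximab vintage".
- Section IV.C gives the purpose: "Each subject will be stratified prior to randomization to ensure MPO- and PR3-ANCA serotypes and duration of rituximab therapy are approximately equal" in the two arms.
- Section VI.C gives the levels: "Randomization will be stratified on ANCA subtype (MPO vs PR3) and rituximab vintage (< 3 years vs > 3 years".

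**Primary comparison.** VI.C states that the difference between the two "treatment strategies will be assessed using the log-rank test". The power analysis in VI.D begins "Using a two-sided logrank test with an alpha level of 0.05". Neither mentions strata or covariates.

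**Other analyses.** The Primary Aim in section II says "Analysis will also be stratified based on ANCA subtype (due to differences in relapse between patients with MPO and PR3 ANCA) and rituximab vintage", with no method and no status. VI.B and IX.C attach one further item to the primary endpoint: "A subgroup analysis will be performed by ANCA subtype". Vintage is not named there.

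**The concern.** Two readings of the Primary Aim are open. If its stratified analysis is meant as the primary test, VI.C and VI.D omit the strata. If it is an addition, which is what the word *also* suggests, the deciding test leaves out the design factors. No section says which p-value decides the trial.

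Stratified permuted blocks remove most of the chance imbalance in subtype between the arms. The unstratified log-rank variance does not take this into account. When subtype predicts relapse, that variance is too large for the design, so the test rejects less often than its nominal 5% under the null. The unstratified test also mixes patients of different risk within its risk sets, which weakens the estimated treatment contrast.

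What is at stake is a small amount of power, and an unresolved choice in the few trials where the two tests fall on opposite sides of 0.05. The trial is open-label and single-centre, and the investigators review its data every 6 months (sections I and IX.B). That is a good reason to settle the choice in writing beforehand.

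**Working it through.** **1. The plan's own sample size.** VI.D gives 15% and 30% relapse, two-sided alpha 0.05, 80% power, 36 months of enrolment and 180 patients. Section V.A gives close-out 36 months after the last entry. Assumptions: the risks are 36-month risks, relapse times are exponential, allocation is 1:1 and there is no dropout.

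- Hazard ratio: ln(0.85)/ln(0.70) = 0.456.
- Events (Freedman): (1.960 + 0.842)² × [(1 + 0.456)/(1 − 0.456)]² = 56.1, rounded up to 57.
- Event probability with uniform accrual: 1 − (0.85 − 0.7225)/0.1625 = 0.2155 and 1 − (0.70 − 0.49)/0.3567 = 0.4112. The mean is 0.3134.
- N = 56.1/0.3134 = 179, or 57/0.3134 = 182 with rounded events.

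This reproduces 180 from an unstratified formula. The figure is not in dispute.

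**2. The two tests.** With U the observed minus expected events in one arm and V its hypergeometric variance, the unstratified test rejects when |U|/√V > 1.96. The stratified test computes U and V within each of the four subtype-by-vintage strata, sums each over strata, and uses the same rule.

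**3. Simulation set-up.** The documents give neither the size of the subtype effect nor the stratum shares, so these are assumed.
- PR3:MPO relapse hazard ratio 2, 3 or 4; 50% PR3; vintage split 50:50 and not prognostic unless stated.
- Blocks of 4 within stratum, N = 200, accrual and close-out as in step 1, no dropout.
- Each arm's baseline hazard is solved so that its overall 36-month risk is 30% or 15% (both 30% under the null). Example at subtype HR 3: with x the MPO 36-month relapse-free probability, (x + x³)/2 = 0.70 gives x = 0.8294 and (x + x³)/2 = 0.85 gives x = 0.9204. The within-stratum hazard ratio is then ln(0.9204)/ln(0.8294) = 0.44.
- 60,000 null and 40,000 alternative trials per scenario. Monte Carlo SE is about 0.09 points for type I error, 0.18 for power and 0.06 to 0.10 for the paired power difference.

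**4. Main results** (losses taken before rounding):

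| Subtype HR | Type I error, unstratified | Power, unstratified | Power, stratified | Loss (points) | Tests disagree at 0.05 (alternative) |
|---|---|---|---|---|---|
| 2 | 4.5% | 85.9% | 86.5% | 0.6 | 2.3% |
| 3 | 3.8% | 85.8% | 87.7% | 1.9 | 3.1% |
| 4 | 3.4% | 85.4% | 88.4% | 3.1 | 3.9% |

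Type I error of the stratified test is 5.0% to 5.1% throughout. With no subtype effect the tests still disagree in 1.7% of trials, so the excess is 0.6, 1.4 and 2.2 points.

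**5. Sensitivity of the loss** (points; subtype HR 2, 3, 4 unless stated):
- Only the inferior arm calibrated, within-stratum HR 0.456: 0.7, 2.3, 3.5.
- Fixed 36-month follow-up: 0.9, 2.1, 3.1 (power 73.5% to 74.4% unstratified, 74.4% to 77.5% stratified).
- Assumed 30% dropout per 36 months: 0.6, 2.2, 3.9 (75.9% to 76.6% against 77.2% to 79.8%).
- 30% or 70% PR3 at subtype HR 3: 2.5 or 1.2.
- Blocks of 2, 6 or 8 at subtype HR 3: 1.9 to 2.2.
- Vintage also prognostic (assumed HR 2): 0.7, 1.5, 3.0 at subtype HR 1, 2, 3.

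**6. Cost when neither factor is prognostic.** Power is 86.2% unstratified against 85.9% stratified, a cost of 0.3 points. With 30% dropout the cost is 0.7 to 0.8. Sparse strata (30% PR3, 20% in one vintage group) leave this at 0.3 and 0.7.

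**The case against.** The Primary Aim already commits the trial to a stratified analysis on exactly these two factors. An unstratified primary test with a stratified supporting one is coherent and valid, and it matches the formula that reproduces 180. On that view only a label is missing. At N = 200 without dropout the unstratified test keeps 85% to 86% power, above the planned 80%. The size of the loss rests on assumed subtype effects: at hazard ratio 1.5 the two powers are 85.8% and 86.0%, which is no material difference.

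Nor is the gain uniform. Section I sets different re-dosing triggers for MPO and PR3, so the treatment effect may differ by subtype. With arm hazard ratios of 0.3 in MPO and 0.6 in PR3, stratifying loses 0.7 points at subtype HR 2 and gains 0.8 at HR 3. With 0.9 in MPO and 0.35 in PR3 it gains 1.5 and 4.2. Finally, the strata have gaps. A vintage of exactly 3 years belongs to neither level, and the entry criteria admit patients positive for both MPO and PR3.

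Much of this stands: the effect is small, its size is uncertain, and no error in the trial's conclusion follows. It does not remove the point. The missing label decides which p-value counts. The power margin depends on horizon and dropout, as step 5 shows. Under unequal effects the worst cost found is about 0.8 points, against gains of up to about 4. Using strata as assigned at randomisation gives every patient a stratum despite the gaps.

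**Conclusion.** The concern holds. The primary test is written without strata, and the role of the Primary Aim's stratified analysis is undefined. The textual gap is certain; the size of the loss is conditional. For assumed subtype hazard ratios of 2 to 4 the unstratified test runs at 3.4% to 4.5% type I error and gives up about 0.6 to 3.1 points of power at N = 200. The loss is up to 3.9 points with 30% dropout and close to nil if the subtype effect is weak. These figures also assume the 36-month horizon and, apart from the unequal-effect runs, the same treatment effect in both subtypes. The unstratified test is valid, so this should be corrected but does not threaten the trial.

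**What to change.** In VI.C, state that the primary test is the two-sided log-rank test of time from randomisation to first BVAS/WG ≥ 2, stratified by ANCA subtype and rituximab vintage as assigned at randomisation. Give the hazard ratio and 95% confidence interval from a Cox model stratified the same way, so that the estimate matches the test. Report the unstratified log-rank test as a sensitivity analysis. Keep the ANCA-subtype comparison as the subgroup analysis already planned.

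It would help to record in the same place how patients with exactly 3 years of vintage and double-positive patients are assigned to strata.

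The core change is two sentences. Both factors are already recorded for randomisation, so no data or patients are added. The statistical price is the small loss in step 6 if neither factor is prognostic, or up to about 0.8 points if the treatment effect differs by subtype in the unfavourable direction.

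### One 0.05 significance rule covers all nine secondary endpoints without multiplicity control or an exploratory label: about a 37% chance of a false claim if tests are independent and all null, about 27–35% with moderate correlation

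*Combined protocol and SAP*

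**What the plan says.** Section VI.C gives t or Wilcoxon tests for continuous data, chi-square or Fisher tests for categorical data and the log-rank test for relapse. It closes with a single threshold: P "values of 0.05 will be considered significant". The sentence names no endpoint and gives no sidedness.

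Section VI.D is specific to relapse: "Using a two-sided logrank test with an alpha level of 0.05", with "a projected relapse risk of 15% in the superior group and 30% in the inferior group". No other endpoint has a power statement.

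Section VI.B lists one primary endpoint (flare, with a subgroup analysis by ANCA subtype) and nine secondary endpoints:

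1. serious adverse events (SAEs), including late-onset neutropenia
2. a composite of flare and SAEs
3. rituximab use
4. organ damage (VDI)
5. quality of life
6. major relapse
7. survival
8. hypogammaglobulinemia
9. all infections

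The fifth is one list item with two instruments and repeated measurement: "Patient quality of life assessment using the SF-36v2 and EQ-5D-5L surveys every 6 months".

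Three of the nine are also formal aims in Section II. Secondary Aim 2 asks which strategy "is associated with a greater composite of disease relapse" and SAEs. Section V.E says that efficacy and toxicity will be assessed through both the primary and the secondary endpoints. No section gives a testing order, an adjustment or a statement that secondary results are exploratory.

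**The concern.** Read literally, the rule lets any of the nine secondary comparisons be called significant at 0.05. The more comparisons are judged this way, the likelier it is that chance alone produces at least one such label. The secondary endpoints are not incidental: SAEs, the composite and rituximab use are formal aims, and Section II expects the utilization result to guide wider use of the dosing strategies. A label earned by chance on SAEs, damage or quality of life could therefore influence the choice between strategies.

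The composite raises a separate matter of interpretation. Because it contains the primary event, a relapse difference alone could produce a second significant result that adds little new information.

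**Working it through.** **The plan's own figures.** The document states no familywise error rate, so there is none to reproduce. Its only related figure is the sample size, "180 patients are required to detect a significant difference with a power of 0.80". HR = ln(0.85)/ln(0.70) = 0.456, and Freedman's formula gives 57 events. Assume 1:1 allocation, exponential times, risks that refer to 36 months, uniform accrual over 36 months and 36 further months of follow-up. The mean event probability is then 0.313, and N = 57/0.313 = 182, close to 180. This shows only that the calculation concerns relapse and spends the full two-sided 0.05 there. It says nothing about the secondary endpoints.

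**Inputs.** Level 0.05 per test (VI.C); nine secondary endpoints (VI.B); three secondary aims (II). One test per endpoint is an assumption, because no analysis time point or questionnaire score is named.

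**Step 1: independent tests, all nulls true.** Chance of at least one P below 0.05 = 1 − 0.95^k.

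- Three aims: 1 − 0.95^3 = 1 − 0.857 = 14%
- Eight tests: 1 − 0.95^8 = 1 − 0.663 = 34%
- Nine tests: 1 − 0.95^9 = 1 − 0.630 = 37%
- Ten tests (the two questionnaires tested separately): 1 − 0.95^10 = 1 − 0.599 = 40%

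**Step 2: correlated tests.** The endpoints overlap. The composite contains flare and SAEs, major relapse lies within flare, and serious infections and deaths overlap with SAEs. The document gives no correlations, so a range is assumed. Take Z_j = √r·C + √(1−r)·E_j, with C and E_j independent standard normal, and reject if |Z_j| > 1.96.

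| Tests | r = 0 | r = 0.2 | r = 0.3 | r = 0.5 |
|---|---|---|---|---|
| 8 | 34% | 32% | 30% | 25% |
| 9 | 37% | 35% | 33% | 27% |
| 10 | 40% | 38% | 35% | 29% |

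The eight-test row leaves out rituximab use. The arms follow different dosing rules (Section I), so equal use is doubtful as a null. For nine tests under any dependence, the limits are 5% (all tests identical) and 9 × 0.05 = 45%.

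**Step 3: rare events.** With an assumed 100 patients per arm, the actual size of Fisher's exact test is 0.5% at a 2% event risk and 2.1% at 5%. The document gives no rates for survival or hypogammaglobulinemia. If both had a size of 0.5%, nine independent tests would give 1 − 0.95^7 × 0.995^2 = 1 − 0.698 × 0.990 = 31%.

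**Step 4: cross-check with the overlap built in.** This simulation used 2,000 runs per setting and 100 patients per arm. Assumed risks were flare 22.5%, SAE 20%, death 4%, hypogammaglobulinemia 4% and infection 50%. The composite and major relapse were derived from their components, Fisher's test was used for sparse tables, and three endpoints were continuous. The result was 34%, 33%, 31% and 27% at latent correlations of 0, 0.2, 0.4 and 0.6.

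**Step 5: what pushes the other way.** Visits every six months for quality of life and VDI, SF-36v2 domains and the ANCA-subtype analysis could each add tests under the same rule. Their number is not specified, so this effect cannot be sized.

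**The case against.** The strongest reply is that the trial has one primary endpoint, powers only that endpoint and tests it at 0.05. Unadjusted secondary tests leave its error rate alone, and many readers treat secondary P values as nominal anyway. The part about the primary stands in full. The part about readers does not settle the matter, because the plan's own sentence attaches the word significant to every comparison.

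A reader might infer that the chance of a false secondary claim simply is 37–40%. The documents do not support that. The 37% needs independence, nine true nulls and exactly 5% per test; the endpoints visibly overlap, a null for rituximab use is doubtful, and Fisher's test is conservative for rare events. The 40% needs ten tests, and no section says that the two questionnaires will be tested separately.

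A reader might also infer that the composite creates false positives. If relapse truly differs, a difference in a composite containing relapse may be real; the difficulty is its interpretation.

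Nor does any section say that secondary results will be presented as established. The plan permits the label; whether it would be used that way is not stated.

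Finally, a formal testing hierarchy has a price. If relapse does not differ, it blocks claims on SAEs and rituximab use, when those would matter most for choosing a strategy. In a fixed order, a non-significant SAE test, for which no power is planned, also blocks Aim 3. The composite would remain in the chain. This objection stands, so a hierarchy is not put forward as necessary.

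**Conclusion.** The point holds in conditional form and should be corrected. As written, the plan allows significance claims on nine secondary endpoints with no control and no exploratory label. With one test per endpoint and all nine nulls true, the chance of at least one false claim is about 37% under independence and about 27–35% at common correlations of 0.5 to 0.2. If rituximab use truly differs, the range for the other eight at those correlations is about 25–32%. Even 25% is five times the nominal 5%. The exact figure is unknown: sparse Fisher tests lower it, and unspecified time points, domains and subgroup tests raise it.

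The stronger reading, that the trial's main conclusion is exposed to inflated error, fails. The primary log-rank comparison keeps its 5% type I error however the secondary endpoints are handled.

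**What to change.** Replace the closing sentence of VI.C with wording such as: *The two-sided 0.05 significance level applies only to the primary log-rank comparison of time to relapse. All secondary endpoints, including the composite of relapse and serious adverse events, will be reported as estimates with unadjusted 95% confidence intervals. Any P values for them are nominal and will not be used to claim statistical significance.*

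Naming the composite matters because it contains the primary event. The change leaves sample size, visits, data collection and the primary test as they are, and all safety outcomes are still reported. The cost is that no secondary result can be called statistically significant.

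If the sponsor wants confirmatory claims for Secondary Aims 1 to 3, one procedure, either a fixed hierarchy after the primary or Holm, can be prespecified for those three. The two behave differently, so one must be named in advance. That is a matter of choice and is not needed to close the gap.
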